5.5 Analysis of other covariate effects

Covariates may be assessed for potential confounding (due to imperfect randomization balance) or effect modification (subgroup efficacy heterogeneity) using multiple logistic regression. Covariates to be considered will include age, race, sex, site, and severity scores at baseline (i.e., APACHE II, Anaya¹³ and LRINEC¹⁴). Other baseline variables in which randomization failed to produce adequate balance between groups (if any) will be examined in supporting analyses. This will be done through stratified analyses or multiple logistic regression. Covariate effects on estimates and interactions with treatment effects will be assessed as needed to evaluate treatment effect heterogeneity. Results from all subgroup analyses will be considered supportive and/or hypothesis-generating.

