Protocol Title	Phase III, randomized, group, study of AB103 a necrotizing soft tissue in ACCUTE (AB103 Clini Necrotizing Soft Tissue	double-blind, placebo-controlled, parallel- as compared to placebo in patients with ifections (NSTI) cal Composite Endpoint Study in Infections)
Location(s)	A multicenter study, that qualified participating sit	will be conducted in approximately 75 es in the US and France
Phase of Development	Phase 3	
Study population	Patients clinically diagno (NSTI) who are schedule their standard of care (So subsequently have a surg	sed with necrotizing soft tissue infections d for an urgent surgical intervention as part of C) for the treatment of their infection and who ically confirmed diagnosis of NSTI.
Study Objectives	 Primary objective: To demonstrate the efficacy of AB103 as compared to placebo, in patients diagnosed with NSTI, using a clinical composite success endpoint: The NSTI clinical composite score, NICCE (Necrotizing Infections Clinical Composite Endpoint) will be defined as the primary end point which will be composed of the following patient outcomes (i) Alive at Day 28, (ii) Day 14 debridements ≤3 (iii) No amputation done after the first debridement (iv) Day 14 modified SOFA (mSOFA) score ≤1 (mSOFA includes respiratory, cardiovascular, central nervous system (CNS), renal, and hematologic organ components but not hepatic/liver component) (v) Reduction of ≥3 score points between Baseline and Day 28, COFA 	
	Component	NICCE
	Survival	Alive at Day 28
	Local component	 ≤3 debridements throughout Day 14 No amputation beyond first debridement
	Systemic component	 mSOFA score of ≤1 at Day 14 Reduction of ≥3 score points between Baseline and Day 14 mSOFA score
	To be considered a succe NICCE. A two-sided $\alpha=0$ relative to placebo for the	ss, patients must meet all components of the 0.01 will be used to test superiority of AB103 e primary endpoint (NICCE).

Conditional co-primary end point:
To demonstrate the efficacy of AB103 as compared to placebo, in patients diagnosed with NSTI, using a modified clinical composite success endpoint that includes (i) Alive at Day 28, (ii) Day 14 debridements \leq 3 (iii) No amputation done after the first debridement. To be considered a success, patients must meet all 3 components of this modified composite endpoint.

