9.2.7 Analysis Of Other Covariate Effects

Covariates will be assessed for potential confounding (due to lack of perfect randomization balance) or effect modification (subgroup efficacy heterogeneity) using multiple logistic regression. Covariates will include but are not limited to age, race, sex, site, and clinical severity scores at baseline. Other baseline variables in which randomization failed to

produce balance between groups will be examined in supporting analyses. This will be done through stratified analyses and multiple logistic regression. Covariate effects on estimates and interactions will be assessed to see if there is evidence of efficacy heterogeneity. Results from all subgroups analyses will be considered hypothesis-generating.

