2.5 Randomization

290 patients will be recruited into the study and randomized to either Reltecimod 0.50 mg/kg or placebo in a 1:1 ratio. Randomization will be within site stratified by presence (+) of a diagnosis of Fournier's Gangrene versus absence (-) and whether the screening mSOFA score is >4 (+) or 3-4 (-) (See Tables 14.1.1.1 to 14.1.1.4). In the Retrospective Study analysis set with screening mSOFA \geq 3 (N=69), the median mSOFA value was 4 and 46.6% had values >4. Thus, the stratification for mSOFA is expected to roughly reflect a median split.

Four computer generated, blocked randomization lists will be provided for each site corresponding to the cross-tabulation of Fournier's Gangrene (+ vs -) and baseline mSOFA >4 (+ vs -) category status. Within each block, half of the assignments will be to active drug and half to placebo, in random order. Block sizes will be randomly varied as an additional masking feature.

The following will be done to insure balance through randomization. Every initial randomization code will end in '-1'. If a randomization code is used but the patient does not receive drug due to lack of confirmatory surgical NSTI diagnosis³, then the randomization code is not reused. Instead, the next patient from same stratum, (+,+), (+,-), (-,+), or (-,-) as the non-dosed patient, will receive the same allocation and the same randomization code except that the new code will end in '-2' while the old code ended in '-1'. In this way, randomization codes are not re-assigned which can cause confusion but the same drug allocation using the digits prior to the '-' are used, thereby preserving balance.

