SOFA – Sequential Organ Failure Assessment score

Can range from 0 -24

Respiratory system:

PaO ₂ / FiO ₂ (mmHg)	SOFA score
=>400	0
< 400	1
< 300	2
< 200 and mechanically ventilated	3
< 100 and mechanically ventilated	4

Nervous System:

Glasgow Coma Scale	SOFA score
15	0
13-14	1
10-12	2
6-9	3
< 6	4

Cardiovascular System

Mean Arterial Pressure (MAP) OR administration of vasopressors (mcg/Kg/minute)	SOFA score
$MAP \Rightarrow 70 \text{ mmHg}$	0
MAP < 70 mmHg	1
Dopamine <= 5 OR Dobutamine any dose	2
Dopamine > 5 <=15 OR epinephrine <=0.1 OR norepinephrine <= 0.1	3
Dopamine > 15 OR epinephrine > 0.1 OR norepinephrine > 0.1	4

MAP= (Systolic pressure + (2*Diastolic pressure))/3

Liver:

Bilirubin (mg/dl)	SOFA score
<1.2	0
1.2-1.9	1
2.0-5.9	2
6.0-11.9	3
>= 12.0	4

Coagulation:

Platelets x 10 ³ /mcl	SOFA score
=>150	0
< 150	1
< 100	2
< 50	3
< 20	4

Renal System:

Creatinine (mg/dl) (or urine output)	SOFA score
<1.2	0
1.2 - 1.9	1
2.0 - 3.4	2
3.5 - 4.9 (or < 500 ml/day)	3
>=5.0 (or < 200 ml/day)	4

Anaya score

Can range from 0 - 12

Variable on admission	Points
Heart Rate > 110 beats per minute	1
Temperature < 36.0 °C	1
Serum Creatinine > 1.5 mg/dl	1
Age > 50	3
White blood cells count > 40,000/mcl	3
Hematocrit > 50%	3

LRINEC – Laboratory Risk Indicator for Necrotizing Fasciitis

Can range from 0 - 13

	П
Variable, Units	Score
C-Reactive Protein mg/L	
< 150	0
>= 150	4
Total White Blood cells count per mm ³	
< 15	0
15 - 25	1
>25	2
Hemoglobin g/dL	
>13.5	0
11.0 – 13.5	1
< 11	2
Sodium mmol/L or meq/L	
>= 135	0
< 135	2
Creatinine µmol/L (mg/dL)	
<= 141 (1.595)	0
>141 (1.595)	2
Glucose mmol/L (mg/dL)	
<=10 (180.18)	0
>10 (180.18)	1

16 Appendix 6: Randomization Program: SAS call to R program

```
proc format;
value treatment fmt
  1 = 'Placebo'
  2 = 'Active'
run;
proc iml;
submit / R;
library(doParallel)
site hold <- seq(10, 49, by = 1)
strata hold <- c(1,2,3,4)
block 4 < -c(1,1,2,2)
block_6 <- c(1,1,1,2,2,2)
theseed = 42
set.seed(theseed)
site loop <- foreach (si = site hold, .combine=rbind) %do% {</pre>
  site num <- si
  strata loop <- foreach (s = strata hold, .combine=rbind) %do% {</pre>
    strata num <- s
    full block <- foreach (i =1:5, .combine=rbind) %do% {</pre>
      get random block <- rbinom(1, 1, 0.5)</pre>
      if (get random block == 1) {
        block <- sample(block 6, 6, replace = FALSE)
      if (get random block == 0) {
        block <- sample(block 4, 4, replace = FALSE)</pre>
      full block <- as.matrix(block)</pre>

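### Site is listed as a covariate for supporting logistic regressions with no stated handling; entered as ordinary indicators, it would inflate the treatment odds ratio through sparse-data bias alone

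*SAP*

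**What the plan says.** SAP 5.5 states: "Covariates may be assessed for potential confounding (due to imperfect randomization balance) or effect modification (subgroup efficacy heterogeneity) using multiple logistic regression". It continues: "Covariates to be considered will include age, race, sex, site, and severity scores at baseline". On how the results are to be read, it says: "Covariate effects on estimates and interactions with treatment effects will be assessed as needed to evaluate treatment effect heterogeneity". Protocol 9.2.7 is firmer about the list: "Covariates will include but are not limited to age, race, sex, site, and clinical severity scores at baseline". Neither section says whether site is fixed, random, conditioned out or pooled into larger units.

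On size, SAP 2.5 says "290 patients will be recruited into the study and randomized to either Reltecimod 0.50 mg/kg or placebo in a 1:1 ratio", and the protocol synopsis says the study "will be conducted in approximately 75" sites. The randomization program in SAP Appendix 6 loops over site numbers 10 to 49. Allocation is blocked within site: "Four computer generated, blocked randomization lists will be provided for each site".

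Random-effects handling of site does appear in SAP 5.3 and protocol 9.2.6. It is confined there to poolability, and the random-effects logistic regression is run only if site variability proves significant.

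**The concern.** Site is categorical, so on a plain reading multiple logistic regression with site means one intercept per site. With a handful of patients in each, the number of nuisance parameters grows with the number of sites, and unconditional maximum likelihood no longer estimates the treatment log odds ratio without bias. When there is a true effect the estimate is too far from zero. When there is none, the Wald test rejects too often. Neither needs any real difference between sites.

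This matters because of the purpose of SAP 5.5. The section looks at how covariates change the treatment estimate. With site indicators the estimate tends to change even if site is unrelated to outcome, and in the direction that favours the drug when the drug works. A reader could take the shift for confounding that had been corrected.

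**Working it through.** **Inputs from the documents.** 290 patients, 145 per arm (SAP 2.4.1, 2.5). About 75 sites (protocol synopsis), or 49 − 10 + 1 = 40 sites (SAP Appendix 6), used here as a lower figure. Within-site blocks of 4 or 6 in four strata (SAP 2.5, Appendix 6). Success rates 0.60 and 0.40, the SAP's difference of 0.20 centred on 0.5.

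**The plan's own figure.** The documents give no figure for site-adjusted estimates, so the check on inputs is the stated power. With two-sided alpha 0.01 and pooled variance under the null:

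- Critical difference: 2.576 × √(2 × 0.25/145) = 0.1513.
- Standard error under the alternative: √((0.24 + 0.24)/145) = 0.0575.
- Power: Φ((0.20 − 0.1513)/0.0575) = Φ(0.847) = 0.8015, against the stated 80.2%.

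The powers for differences of 0.25 and 0.30 also reproduce (0.9588 and 0.996).

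**Patients per site.** 290/75 = 3.87; 290/40 = 7.25.

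**True odds ratio.** (0.60/0.40) × (0.60/0.40) = 2.25, log 0.811.

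**Simulation.** There were 1,000 trials per setting with zero site effect, so site cannot confound. Assumptions not in the documents: stratum shares of 0.10, 0.37, 0.12 and 0.41, and enrolment that is either equal across sites or skewed (flat Dirichlet). Treatment and site were the only terms in the site models. Odds ratios are exponentiated mean log odds ratios. The last column comes from separate runs at 0.5 against 0.5.

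| Sites, enrolment | Unadjusted OR | Site-indicator OR | Conditional OR | Log OR, indicators ÷ unadjusted | Upward shift over 10%: indicators / conditional | 5% Wald rejection under the null: indicators / conditional |
|---|---|---|---|---|---|---|
| 75, equal | 2.23 | 3.01 | 2.25 | 1.37 | 90% / 28% | 8.2% / 4.6% |
| 75, skewed | 2.29 | 2.69 | 2.30 | 1.20 | 75% / 22% | 7.7% / 5.1% |
| 40, equal | 2.26 | 2.59 | 2.26 | 1.17 | 74% / 15% | 7.7% / 6.1% |
| 40, skewed | 2.26 | 2.47 | 2.25 | 1.11 | 52% / 11% | 6.3% / 4.9% |

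For the first row, ln 3.01 / ln 2.23 = 1.102/0.802 = 1.37. The 10% threshold is an assumption; the plan has no such rule.

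**Precision under the null.** The Monte Carlo standard error at 5% is √(0.05 × 0.95/1,000) = 0.7 points. Rejection of 8.2% is well outside it; 6.3% is about 1.9 standard errors above nominal. A separate set of 1,500 trials per setting gave 8.7% and 7.9% at 75 sites (equal, skewed), and 6.3% and 6.0% at 40. Under the null the mean odds ratio with site indicators stays between 0.99 and 1.01, so the harm there is excess rejection, not a shifted estimate.

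**Information lost.** At 75 equal sites, on average 64.5 sites and 250 of 290 patients remain once sites with no outcome variation drop out.

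**If site effects do exist.** With a site standard deviation of 0.5 on the logit scale, the conditional log odds ratio exceeds the unadjusted one by about 6% in all four settings, which is non-collapsibility and not bias. Site indicators exceed it by 18% to 44%.

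**Random site intercept.** In 500 trials per setting with no site effect, the estimate stays within 1% to 2% of unadjusted, and upward shifts over 10% occur in 0.6% to 4.2% of trials.

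**The case against.** The strongest case against is that the plan does not commit to the biased model. SAP 5.5 is permissive about both the analysis and the covariates, and SAP 1 says the SAP prevails over the protocol, so the firmer wording of protocol 9.2.7 does not govern. The plan's own approach to site, in SAP 5.3, is random effects. No planned table in SAP Appendix 1 reports a site-adjusted logistic estimate: Tables 14.2.1.5 and 14.2.1.6 tabulate results by site, and the model-adjusted NICCE tables use only the Fournier's and mSOFA strata. There is no change-in-estimate rule, and site is not in the subgroup list of SAP 4.6. The size of the bias depends on enrolment, which is not yet known.

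All of this stands, and it limits the consequence. A reader might infer that the trial will publish an exaggerated, supposedly confounding-corrected effect, or that its conclusion is at risk. The documents support neither: success under SAP 2.2 rests on unadjusted chi-square tests of NICCE and CCPE, and the key secondary test in SAP 2.3 is also unadjusted.

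What the objection does not remove is that SAP 5.5 names ordinary logistic regression and names site, with nothing to rule out indicators. SAP 5.3 is conditional on significant site variability and does not bind 5.5.

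A further objection concerns the remedy. Conditional logistic regression also drops sites without outcome variation, and at 75 equal sites it still moves the log odds ratio up by more than 10% in 28% of unconfounded trials. That is right, and it is why a random intercept is preferred.

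**Conclusion.** The point holds as a conditional one about supporting analyses. If site enters as ordinary indicators, the treatment log odds ratio is inflated by about 11% (40 sites, skewed enrolment) to 37% (75 equal sites) when the true rates are 0.60 and 0.40 and site has no effect. The nominal 5% Wald test rejects in about 6% to 9% of null trials, with the excess clearest at 75 sites. That such a shift would in fact be read as confounding is an inference, since the plan sets no rule for declaring it; the wording leaves room for it.

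The sizes rest on the assumed enrolment patterns and stratum shares, and on models containing only treatment and site. Interactions with site were not examined, and the random intercept was checked only without site effects.

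**What to change.** In SAP 5.5 and protocol 9.2.7, remove site from the list of ordinary logistic covariates. Add that, where adjustment for site is wanted, the responder endpoint will be analysed by logistic regression with a random site intercept, cross-referring to SAP 5.3. State the intercept explicitly: SAP 5.3 speaks of heterogeneity in treatment effects, whereas protocol 9.2.6 speaks of a random site effect.

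Conditional logistic regression stratified by site can be named as an alternative, noting that it discards sites where all patients succeed or all fail. Add one sentence saying that, if sites differ, a site-adjusted odds ratio will differ from the unadjusted one through non-collapsibility, so a difference alone is not evidence of confounding.

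The cost is a few lines of wording, best settled before unblinding. It needs no new data, only standard software, and changes no confirmatory test.

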5.6 Multiplicity

The overall study success criterion, agreed upon with FDA, is to simultaneously observe $p \le 0.01$ for the primary endpoint (NICCE) and $p \le 0.05$ for the conditional co-primary endpoint (CCPE). Therefore, there is no concern regarding type 1 error inflation due to multiplicity for the overall study success criterion.

To control type 1 error for the key secondary efficacy endpoint, superiority of Reltecimod relative to placebo in terms of freedom from durable loss of renal function among those presenting with Stage 2 or Stage 3 AKI will only be interpreted as a confirmatory hypothesis test if p \leq 0.01 for the primary endpoint (NICCE) and p \leq 0.05 for the co-primary endpoint (CCPEP). Otherwise, treatment group comparisons in terms of the key secondary efficacy (AKI) endpoint will be interpreted as a descriptive endpoint. An unadjusted chi-square test using a two-sided type 1 error of α =0.05 will be used to test superiority of Reltecimod relative to placebo for the key secondary AKI endpoint.

13

¹³ Anaya, D. A., E. M. Bulger, et al. Predicting Death in Necrotizing Soft Tissue Infections: A Clinical Score. Surgical Infections 2009: 10(6): 517-522.

Wong, C. H., L. W. Khin, et al. The LRINEC (Laboratory Risk Indicator for Necrotizing Fasciitis) score: a tool for distinguishing necrotizing fasciitis from other soft tissue infections. Crit Care Med 2004: 32(7): 1535-1541.

There will be no attempt to control type 1 error for other secondary NSTI or AKI endpoints.

5.7 Descriptive Analyses of Additional Secondary Endpoints

Additional secondary endpoints have been specified from several domains including individual components of the primary composite endpoint (NICCE), time to resolution of organ dysfunction, critical care and hospital stay parameters (ICU and ICU-free days, ventilator days and -free days, vasopressor days and -free days, hospital LOS), clinical local parameters (debridement history variables), and clinical systemic parameters (mSOFA over time, incidence and recovery from AKI). Analyses for these endpoints will generally be descriptive, with emphasis on characterizing clinical effect sizes¹⁵. Nominal p-values will be presented in some cases as an aid to interpretation but with no adjustment for multiplicity. Categorical outcomes will be summarized using counts and percentages with nominal p-values determined through chi-square or exact methods. Critical care and hospital stay endpoints will be compared using non-parametric approaches including using concordance statistics (c-stat) to characterize clinical effect size and Wilcoxon rank sum tests to determine nominal statistical significance. The c-stat is the probability that a randomly selected patient treated with Reltecimod has a better (e.g., greater number of free-days) than a randomly selection patient treatment with placebo. Methods appropriate for time-to-event endpoints including survival and life-table methods will be used for time-to-organ dysfunction resolution endpoints. Additional analyses of mSOFA over time will employ methods appropriate for longitudinal data. For these analyses, statistical testing and estimation will be based on a Mixed Model Repeated Measures (MMRM)¹⁶.

5.8 Analysis of Longitudinal Outcomes

Supporting analysis will be performed for mSOFA over time using the Mixed Model for Repeated Measures (MMRM) analysis of covariance (ANCOVA) approach¹⁷. The following baseline covariates will be included in the primary MMRM analysis to mSOFA over time.

- Day 0 mSOFA = 3-4 versus > 4
- Presence versus absence of Fournier's gangrene
- APACHE II score
- mSOFA Day 1
- Presence of Stage 2/3 AKI at Screening

mSOFA Day 1 is included because this score reflects patient status post initial surgery. In addition to this variable, the Day 0 stratification factors are included to reflect the experimental design. Screening APACHE II is included to account for variation in medical status at screening. Presence of Stage 2/3 AKI at screening is included given emerging evidence of its impact on clinical outcomes. Inclusion of covariates can increase power by explaining variance and also help with the implicit imputation of missing values that is inherent in the MMRM approach.

MMRM is a direct likelihood approach that requires specialized statistical software for optimizing the likelihood function. For this study, all MMRM parameters will be estimated using SAS PROC MIXED [SAS Institute¹⁸]. The MMRM model is notable for its ability to include all available data from all eligible subjects and does not require their exclusion as in 'complete case analysis'

¹⁵ Cohen, J. Statistical power analysis for the behavioral sciences (2nd ed.). New York, Academic Press, 1988.

¹⁶ Verbeke G and Molenberghs G. Linear Mixed Models for Longitudinal Data, New York: Springer, 2000.

¹⁷ Verbeke G and Molenberghs G. Linear Mixed Models for Longitudinal Data, New York: Springer, 2000.

¹⁸ SAS Institute, Cary NC.

or arbitrary assignment of values as in 'last-observation-carried-forward' (LOCF). The MMRM model generally includes a factor for treatment group by time interaction in order to allow group differences in mean value to vary over time. Inclusion of outcome data from all time points informs the implicit imputation of values missing at specific time points through the outcome covariance matrix. Inclusion of baseline covariates has potential for further reduction of potential bias due from missing values.

Specifically, MMRM will be used to compare mean values at each time point between the Reltecimod 0.50 mg/kg dose and placebo with a key emphasis on the Day 14 contrast. Model parameters will be estimated using Restricted Maximum Likelihood¹⁹,²⁰(REML) as implemented Proc Mixed [SAS Institute²¹]. A generalized Satterthwaite approximation will be used to determine accurate estimates of denominator degrees of freedom for statistical tests²². Analyses will characterize changes over time as functions of the baseline value, treatment group, time, and treatment by time interaction. Between-group differences at each time point will be evaluated using contrasts derived from mixed model parameter estimates. This approach produces inferences that are valid under the assumption of 'missing at random' (MAR). MAR based inferences are valid under broader assumptions than complete case analysis or analyses utilizing LOCF²³. The modeling results will be graphically presented by plotting the individual least squares predicted mean values.

